## **10.2 Primary Efficacy Analysis**

The primary efficacy endpoint is the proportion of subjects with a  $\geq 90\%$  reduction from baseline in Psoriasis Area and Severity Index (PASI 90) at Week 24.

The primary null hypothesis is that risankizumab is not different from FUMADERM® in achieving  $\geq 90\%$  reduction from baseline in the Psoriasis Area and Severity Index score (PASI 90) at Week 24.

The primary endpoint will be analyzed in the ITT Population. The difference in proportion of subjects achieving PASI 90 between treatment arms will be estimated and tested using the two-sided Cochran-Mantel-Haenszel risk difference estimate stratified by prior phototherapy exposure at level of significance 5%.

Non-responder imputation will be used as the primary approach for missing values. LOCF and MI will be performed as sensitivity analyses.

## **10.3 Secondary Efficacy Analyses**

The secondary endpoints will be analyzed in the ITT Population. The following null hypotheses will be tested using two-sided tests with a type I error of 0.05.

The secondary endpoints are as follows:

- Proportion of subjects with a PASI 50/75/90/100 response at Week 4, 8, 12, 16, 20 and 24.
- Change from baseline in PASI at Week 4, 8, 12, 16, 20 and 24.
- Change from baseline in BSA affected by psoriasis at Week 4, 8, 12, 16, 20 and 24.
- Proportion of subjects with a sPGA of 0 or 1 at Week 4, 8, 12, 16, 20 and 24.
- Proportion of subjects with sPGA of 0 at Week 4, 8, 12, 16, 20 and 24.
- Change from Baseline in PPASI Total Score at Week 16 and 24.
- Change from Baseline in PSSI Total Score at Week 16 and 24.
- Change from Baseline on the NAPPA-CLIN Total Score at Week 16 and 24 (for all subjects and for subjects with NAPPA-CLIN > 0 at baseline).
- Change from Baseline on the NAPSI at Week 16 and 24 (for all subjects and for subjects with NAPSI > 0 at baseline).
- Change from Baseline in Psoriasis Symptom Scale (PSS) total score at Week 16 and 24.
- Proportion of subjects achieving PSS (0) at Week 16 and 24.
- Change from Baseline in DLQI total score at Week 16 and 24.
- Proportion of subject achieving DLQI (0, 1) at Week 16 and 24.
- Change from Baseline in SF-36 PCS and MCS Scores at Week 16 and 24.
- Change from Baseline in PBI at Week 16 and 24
- Change from Baseline on HADS at Week 16 and 24.
- Change from Baseline on PtGA at Week 16 and 24.
- Change from Baseline in EQ-5D-5L Index, EQ-5D Utility Index and VAS at Week 16 and 24.

The order of the secondary endpoints does not reflect a ranking.

**10.4 Handling of Multiplicity**

The order of the secondary endpoints does not reflect a ranking and secondary endpoints will not be used for confirmatory interpretation, thus no adjustment for multiplicity will be done.

**10.5 Efficacy Subgroup Analysis**

To evaluate the consistency of the efficacy over demographic and other baseline characteristics, summaries and analyses will be performed for the following subgroups for the primary efficacy endpoint.

- Age (< 40 years,  $\geq 40$  –  $< 65$  years,  $\geq 65$  years)
- Sex (male, female)
- Race (white, non-white)
- Smoking (current, former or never)
- BMI (normal:  $< 25$ , over weight:  $\geq 25$  –  $< 30$ , obese:  $\geq 30$ )
- Baseline PASI score (by median)
- Baseline sPGA ( $\leq 2, 3, 4$ )
- Prior Phototherapy (yes/no)

**11.0 Safety Analysis****11.1 General Considerations**

Safety evaluations include AE monitoring, physical examinations, vital sign measurements, and clinical laboratory testing (hematology, chemistry, and urinalysis) as a measure of safety and tolerability for the entire study duration. Safety summaries will be provided using the safety population as defined in Section 5.1. Pairwise comparisons of risankizumab vs FUMADERM® will be performed in the Safety Population. AEs will be analyzed using Fisher's exact test, only P values  $\leq 0.100$ , when rounded to three digits, will be presented.

Missing safety evaluations will not be imputed.

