## **4.0 Study Objective**

The objective of this study is to compare the efficacy and safety of SC risankizumab and oral FUMADERM® provided as study medication in subjects with moderate to severe plaque psoriasis who are naïve to and candidates for systemic therapy.

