### **8.1.5 Analysis of Safety**

All safety analyses will be performed in the safety population.

Treatment-emergent adverse events are defined as events with an onset date on or after the first dose of study drug until 15 weeks (105 days) following the last dose of risankizumab or 1 week (7 days) after the last dose of FUMADERM® provided as study medication or until rollover into the extension study. In a sensitivity analysis, adverse events with an onset date until 7 weeks (49 days) after the last dose of FUMADERM® provided as study medication or until rollover into the extension study will be included.

SAEs and protocol-related non-serious AEs with onset after informed consent but before the first study drug administration will be considered as pretreatment events and reported separately.

Adverse events will be tabulated by system organ class and preferred term, whereby the most current implemented MedDRA dictionary will be used. Also, summaries by severity and relationship to study drug will be done. Certain adverse events, like serious or severe, leading to discontinuation, will be listed and described in detail. Adverse events of interest for treatment with biologics will be defined in the statistical analysis plan and analyzed separately.

Adverse events will be summarized by frequency and percentage and presented by treatment group, statistical comparisons will be performed using Fisher's exact test.

Other safety variables like laboratory data and vital signs will also be described by descriptive statistics for each treatment group. Treatment comparisons will be performed by one way ANOVA. In addition, shift tables and listings will be provided for abnormal values, whereby the normal range of the analyzing laboratory will be used.

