### **4.0                   Study Objectives, Design and Procedures**

#### **4.1                   Objectives**

The objective of this study is to compare the efficacy and safety of subcutaneous (SC) risankizumab and oral FUMADERM® provided as study medication in subjects with moderate to severe plaque psoriasis who are naïve to and candidates for systemic therapy.

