#### **Summary tables will be presented as follows:**

##### **1. Adverse Event Overview**

The number and percentage of subjects experiencing treatment-emergent adverse events will be summarized for the following adverse event categories.

- Any AE
- Any AE that was assessed as related to study drug by the investigator
- Any severe AE
- Any serious AE (SAE)
- Any SAE that was assessed as related to study drug by the investigator

- Any AE leading to discontinuation of study drug.
- Any AE leading to death.
- Any deaths
- Areas of Safety Interest

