## **Adverse Event per 100 Patient-Years of Exposure**

AEs occurring during the entire study will be presented by event rate per 100 patient-years. These will be presented for any TEAEs, serious adverse events, Areas of Safety Interest.

AEs per 100 patient-years of exposure is defined as the number of AEs divided by the total exposure in 100 patient-years. Note that one event per preferred term per day per subject will be counted in the calculation of the number of AEs (i.e., a preferred term will not be counted twice on the same day for the same subject). See the calculation method below.

$$100 \times \frac{\text{Number of TEAEs}}{\text{Total Patient Years}}$$

where total patient years is defined as the sum of the study drug exposure (defined as date of last dose – date of first dose + 105 days or + 7 / 49 (sensitivity analysis) days for risankizumab or FUMADERM®, respectively) of all subjects normalized by 365.25, and rounded to one decimal place.

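### Adverse events are compared between arms only by a Fisher p-value that is printed when it is 0.100 or less; no effect size or confidence interval is planned

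*SAP*

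**What the plan says.** Protocol 4.0: "The objective of this study is to compare the efficacy and safety" of the two treatments. SAP 4.1 repeats this.

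Protocol 8.1.5 has two elements for adverse events: "Adverse events will be summarized by frequency and percentage and presented by treatment group", and "statistical comparisons will be performed using Fisher's exact test". It sets no threshold for showing a p-value.

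SAP 11.1 adds one: "AEs will be analyzed using Fisher's exact test, only P values" of 0.100 or less, "when rounded to three digits, will be presented". SAP 14.1, which lists changes from the protocol, does not mention this rule.

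SAP 11.2.1 then sets out the tables. For the overview, "The number and percentage of subjects experiencing treatment-emergent adverse events will be summarized for the following adverse event categories". Similar tables follow by system organ class and preferred term, severity, relationship, and Area of Safety Interest. In addition, "AEs occurring during the entire study will be presented by event rate per 100 patient-years", covering all treatment-emergent events, serious events and Areas of Safety Interest. The p-value rule does not touch these figures.

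No risk difference, risk ratio or confidence interval for an adverse event appears in Protocol 8.1.5 or SAP 11.1 to 11.2.3. For categorical efficacy variables, SAP 10.1.1 gives the stratified risk difference, its variance and a 95% CI.

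**The concern.** A trial that sets out to compare safety should report how far apart the arms are and how precisely that is known. Here the only planned between-arm adverse event statistic is a p-value, and it disappears above 0.100. An empty p-value cell covers two different situations: the arms look alike, or they differ noticeably but the numbers are too small to say. Only an interval separates these.

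The filter also selects. Across the system organ class and preferred term rows, repeated in the subgroups of SAP 11.2.3, it prints the smallest unadjusted p-values and omits the rest. SAP 10.4 covers multiplicity for secondary efficacy endpoints only.

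**Working it through.** **Inputs from the documents.** 110 subjects, 55 per arm, 1:1 (Protocol 8.2 and 8.3; SAP 4.3). Display rule: Fisher p of 0.100 or less after rounding to three digits (SAP 11.1). FUMADERM rates in the cited trial: serious events 2.8%, discontinuation for adverse events 24% (Protocol 3.0).

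**Assumed inputs.** All event counts below, and all true rates except the 2.8% and 24%, are illustrations. The calculation assumes that all 55 per arm enter the Safety Population.

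**The plan's own figure.** The documents give no precision figure for adverse events. The stated 94% power (70% vs 35%, two-sided 5%) fixes the arm size. At 55 per arm the exact power of Fisher's test is 94.2%, the continuity-corrected chi-squared formula gives 94.8%, and the uncorrected pooled formula gives 96.6%. So 55 per arm is consistent with the stated power under the first two.

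**Formulas.**
- Fisher p: the sum of hypergeometric probabilities, with margins fixed, of all tables no more likely than the one observed.
- Wilson limits for x/n, with p = x/n and z = 1.96: [p + z²/2n ± z√(p(1-p)/n + z²/4n²)] / (1 + z²/n).
- Newcombe 95% CI for d = p1 - p2: lower = d - √[(p1-l1)² + (u2-p2)²]; upper = d + √[(u1-p1)² + (p2-l2)²].

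**Example A, 29/55 vs 20/55.**
- Wilson: 52.73% (39.79 to 65.31) and 36.36% (24.93 to 49.58); d = 16.36 points.
- Lower: 16.36 - √(12.94² + 13.22²) = 16.36 - 18.50 = -2.1.
- Upper: 16.36 + √(12.58² + 11.43²) = 16.36 + 17.00 = 33.4.
- Fisher p = 0.1245, so not printed.

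**Example B, 5/55 vs 1/55.**
- Wilson: 9.09% (3.95 to 19.58) and 1.82% (0.32 to 9.61); d = 7.27 points.
- Lower: 7.27 - √(5.14² + 7.79²) = 7.27 - 9.33 = -2.1.
- Upper: 7.27 + √(10.49² + 1.50²) = 7.27 + 10.60 = 17.9.
- Fisher p = 0.206, so not printed.

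**Further tables with no printed p-value.**

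| Counts | Fisher p | Difference, points (95% CI) |
|---|---|---|
| 4/55 vs 0/55 | 0.118 | 7.3 (-0.6 to 17.3) |
| 12/55 vs 5/55 | 0.112 | 12.7 (-1.0 to 26.3) |
| 16/55 vs 8/55 | 0.105 | 14.5 (-1.0 to 29.3) |
| 2/55 vs 2/55 | 1.000 | 0 (-9.1 to 9.1) |

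All of these rows have the same empty p-value cell.

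**Largest difference without a p-value.** Running Fisher's test on every pair of counts at 55 per arm, the largest difference that stays above 0.100 is 9 subjects: 9/55 = 16.4 points.

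**How often the p-value would be hidden** (exact binomial sum over all tables):

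| True rates | Probability hidden |
|---|---|
| 5% vs 15% | 57% |
| 10% vs 20% | 66% |
| 30% vs 45% | 59% |
| 0% vs 2.8% | 98% |
| 2% vs 24% | 3% |

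**Windows.** In SAP 11.2.1 the main treatment-emergent window runs to 105 days after the last risankizumab dose but 7 days after the last FUMADERM dose. For a subject dosed to schedule who does not enter the extension study, that is Week 16 + 15 = 31 against Week 24 + 1 = 25. The 49-day sensitivity window gives 24 + 7 = 31 for FUMADERM.

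**The case against.** The strongest reply is that nothing is concealed. The filter acts on p-values alone. The 5/55 vs 1/55 row still prints 9.1% and 1.8%, and anyone can subtract them and compute an interval. The cutoff is prespecified, treats both arms alike and is looser than 0.05, so an empty cell has a defined meaning. There is no safety hypothesis, margin or safety power. Where the documents lead one to expect a large contrast, the rule works: 24% discontinuation against an assumed 2% would be hidden only about 3% of the time. Example B's higher rate of 9.1% is about three times the documented 2.8% serious-event rate on FUMADERM. The list of tables is in a separate document (SAP 17.0), which is not available here.

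Much of this stands, and it rules out two stronger readings. A reader might infer that sizeable differences vanish from the tables. They do not, because the counts, percentages and exposure-adjusted rates are unfiltered. A reader might also infer that the whole safety half of the objective lacks a comparison. It does not: Protocol 8.1.5 plans one-way ANOVA for laboratory and vital-sign data, and SAP 11.3 and 11.4 plan changes from baseline and frequencies of potentially important values, with shift tables for laboratory data.

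What the reply does not supply is the interval. That a reader could calculate it is no reason to leave it out of a trial whose objective is to compare safety, and SAP 11.1 is where the method belongs, whatever the table list contains.

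**Conclusion.** The point holds for adverse events. The plan provides no between-arm estimate with its uncertainty, and the one comparative statistic it does provide is withheld above 0.100. At 55 per arm, an observed difference of up to 16.4 points can appear with no comparative statistic, and an interval for such a row can reach about 33 points. The primary analysis is unaffected and no data are lost, so this is a cheap improvement to reporting.

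The size rests on illustrative counts and assumed true rates, on full arms of 55, and on the Newcombe method. The documents give no expected risankizumab rates for these categories in this trial.

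**What to change.** In SAP 11.1:

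- Add the risk difference with a 95% CI for every row of the adverse event overview and every Area of Safety Interest in SAP Table 6. Name one method, Newcombe or Miettinen-Nurminen.
- Give it under both the main treatment-emergent window and the 49-day FUMADERM sensitivity window. On the main window alone, the interval would put apparent precision on arms observed for different lengths of time.
- Remove the 0.100 display filter for those rows: print all Fisher p-values or none.
- Record the change in SAP 14.1.

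The data are already collected. The cost is SAP wording, wider tables and a little more programming.

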## **11.2 Analysis of Adverse Events**

### **11.2.1 Treatment-Emergent Adverse Events**

Treatment-emergent adverse events (TEAE) are defined as events with an onset date on or after the first dose of study drug until 15 weeks (105 days) following the last dose of risankizumab or 1 week (7 days) after the last dose of FUMADERM® or until rollover into the extension study. In a sensitivity analysis, adverse events with an onset date until 7 weeks (49 days) after the last dose of FUMADERM® or until rollover into the extension study will be included. In this sensitivity analysis, the observation period for TEAEs will be identical for both treatment arms, i.e., up to the 31 week safety follow-up call.

SAEs and protocol-related non-serious AEs with onset after informed consent but before the first study drug administration will be considered as pretreatment events and reported separately. Posttreatment events for FUMADERM® are included in the above sensitivity analysis.

If an incomplete onset date is collected for an adverse event, the event will be assumed to be treatment-emergent unless there is other evidence that confirms that the event is not treatment-emergent (e.g., the event end date is prior to the study drug start date).

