If, during the course of study drug administration, the subject prematurely discontinues study drug use, the procedures outlined for the Early Termination Visit must be completed within 2 weeks after the decision to discontinue, and preferably prior to the initiation of another therapy. However, these procedures should not interfere with the initiation of any new treatments or therapeutic modalities that the Investigator feels are necessary to treat the subject's condition. Following discontinuation of the study drug, the subject will be treated in accordance with the Investigator's best clinical judgment.

A final telephone call will occur for all subjects who do not roll over into the extension study, approximately 15 weeks after the last dose of risankizumab and 7 weeks after the last dose of FUMADERM®, provided as study medication, to determine the status of any ongoing AEs/SAEs or the occurrence of any new AEs/SAEs.

All attempts must be made to determine the date of the last study drug dose and the primary reason for early termination. The information will be recorded on the appropriate eCRF page.

For subjects that are considered lost to follow-up, reasonable attempts must be made to obtain information on the final status of the subject. At a minimum, two phone calls must be made and one certified letter must be sent and documented in the subject's source documentation.

Subjects who discontinue the study prematurely will not be replaced.

Subjects are considered study completers if they have completed the Week 24 visit.

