- b. Subjects that discontinue the study prior to the end of the study will have a follow-up phone call within 15 weeks after the last dose of FUMADERM® provided as study medication for collection of safety data. Subjects that elect to enroll into a separate extension study will not require the Week 31 Follow-Up phone call as part of this trial.
- c. Update history.
- d. Serum pregnancy test in all women at screening and if the urine pregnancy test is positive at any other visit. Urine pregnancy tests are to be performed in all women of child bearing potential prior to administration of study drug at all dosing visits.
- e. Height and weight will be measured at the Screening Visit only (with shoes off).
- f. Targeted laboratory samples should be limited to CBC with differential count (hematology), serum creatinine (substrates) and ALT, AST, gamma-GT and AP (enzymes).
- g. (FSH) To be done at Screening in all women aged ≤ 55 years with no menses for 12 or more months without an alternative medical cause.
- h. Infection screening consists of Hepatitis B Surface Antigen (qualitative), Hepatitis B Surface Antibody (qualitative), Total Hepatitis B Core Antibodies (qualitative), Hepatitis B Virus DNA (quantitative) reflex, Hepatitis C Virus RNA (quantitative) reflex, HIV-1 and HIV-2 Antibody (qualitative), PPD/QuantiFERON-TB.
- i. For FUMADERM® INITIAL and FUMADERM® provided as study medication only.
- j. Prior to other procedures.
- k. SC risankizumab 150 mg at Week 0/Day 1, Week 4 and Week 16. Risankizumab will be administered at the study site by authorized site personnel (e.g., study nurse) after all study procedures have been completed.
- l. Oral FUMADERM® daily starting at Week 0/Day 1 and until Week 24 (the last dose will be in the morning of the day of Week 24 visit). FUMADERM® INITIAL starting at Week 0/Day 1 until Week 2 and FUMADERM® starting at Week 3, both at starting dose of 1 tablet per day, followed by a dose increase of one tablet per week, depending on efficacy response and tolerability. The maximum dose of FUMADERM® of 6 tablets per day should not be exceeded.
- m. PK and ADA samples are collected only from the subjects receiving risankizumab.

---

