#### **4.2                   Design Diagram**

This is a randomized, controlled, multicenter, open-label study with blinded assessment of efficacy to demonstrate the efficacy and safety of SC risankizumab in adult subjects with moderate to severe plaque psoriasis who are naïve to and candidates for systemic therapy as compared with oral FUMADERM® provided as study medication. Eligible male and female subjects with moderate to severe plaque psoriasis will be selected to participate in the study according to the selection criteria. Approximately 110 subjects will be enrolled in this study.

[figure not shown]
The study will include a 30-day screening period and a 24 week active-controlled treatment period followed by a follow-up phone call at Week 31 for subjects that do not elect to enroll into the extension Study M15-997.

After meeting the selection criteria, enrolled subjects will be randomly assigned in a 1:1 ratio to one of two arms as shown below:

- Risankizumab 150 mg SC at Week 0/Day 1, Week 4 and Week 16 or,
- Oral FUMADERM® INITIAL provided as study medication starting at Week 0/Day 1 until Week 2 and FUMADERM® provided as study medication starting at Week 3 until Week 24 (last intake in the morning on the day of Week 24 visit)

A schematic of the study design is shown below in [Figure 1](#).

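### The adverse-event sensitivity analysis gives both arms the same observation period only for on-schedule completers who do not roll over; for early discontinuers the crude proportions still rest on unequal follow-up

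*SAP*

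**What the plan says.** **Windows.** SAP 11.2.1 counts treatment-emergent events on risankizumab "until 15 weeks (105 days) following the last dose of risankizumab". On FUMADERM the main analysis stops 7 days after the last dose; in the sensitivity analysis, events with onset "until 7 weeks (49 days) after the last dose of FUMADERM® or until rollover into the extension study will be included". Rollover ends the period in either arm. The SAP then states that, in this sensitivity analysis, "the observation period for TEAEs will be identical for both treatment arms, i.e., up to the 31 week safety follow-up call".

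**Follow-up.** Protocol 5.1 (Follow-Up Period) derives the Week 31 call from last doses taken on schedule. Protocol 5.4.1 places the final call for everyone who does not roll over "approximately 15 weeks after the last dose of risankizumab and 7 weeks after the last dose of FUMADERM", and Protocol 6.1.4 limits adverse-event collection by the same two intervals. Protocol Appendix C, footnote b, adds that "Subjects that elect to enroll into a separate extension study will not require the Week 31 Follow-Up phone call". The same footnote says that subjects who discontinue early "will have a follow-up phone call within 15 weeks after the last dose of FUMADERM® provided as study medication" and gives no timing for risankizumab.

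**Comparison.** SAP 11.1: "AEs will be analyzed using Fisher's exact test". SAP 11.2.1 also plans event rates per 100 patient-years for any TEAE, serious events and Areas of Safety Interest.

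**The concern.** The main analysis observes risankizumab for 105 days after the last dose and FUMADERM for 7. The sensitivity analysis is the plan's only correction for this in the subject proportions. It works by choosing offsets (15 and 7 weeks) that cancel the gap between the scheduled last doses (Week 16 and Week 24). They cancel only if those doses are taken on schedule. A subject who stops FUMADERM early has a last dose at about the day of stopping, plus 7 weeks. A subject who stops risankizumab early keeps 15 weeks from the last injection.

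Early stopping is where the arms may well differ: Protocol 3.0 cites 24% discontinuation for adverse events on FUMADERM in an earlier trial. Because Protocol 6.1.4 also ends collection at 15 and 7 weeks, the missing FUMADERM time cannot be recovered at analysis. A reader told that the periods are identical would take the crude proportions at face value.

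**Working it through.** **Inputs.** Injections on Rx Days 1, 29 and 113 (SAP 4.2). Last tablet on Day 169 for completers (SAP 4.2). Week w is Rx Day 7w + 1 (SAP 6.0). Offsets 105 and 49 days, or rollover (SAP 11.2.1). Visit windows are ignored.

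**The plan's own figure.** Completers without rollover: risankizumab 113 + 105 = Day 218; FUMADERM 169 + 49 = Day 218; Week 31 is 7 × 31 + 1 = Day 218. The statement is exact for this group.

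**Early discontinuers.** Risankizumab end = last injection on or before the stopping day + 105. FUMADERM end = stopping day + 49.

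| Stop | Stopping day | Risankizumab end | FUMADERM end | Difference (days) |
|---|---|---|---|---|
| Week 2 | 15 | 1 + 105 = 106 | 64 | +42 |
| Week 4, after injection | 29 | 29 + 105 = 134 | 78 | +56 |
| Week 8 | 57 | 134 | 106 | +28 |
| Week 12 | 85 | 134 | 134 | 0 |
| Week 14 | 99 | 134 | 148 | -14 |
| Day before Week 16 injection | 112 | 134 | 161 | -27 |
| Week 16, after injection | 113 | 113 + 105 = 218 | 162 | +56 |
| Week 20 | 141 | 218 | 190 | +28 |

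Over stopping days 1 to 168, risankizumab is observed longer on 140 days, equally on 1 (Day 85) and for less time on 27 (Days 86 to 112). The mean difference is +23.8 days.

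**Rollover.** Only Week 24 completers are offered the extension (Protocol 5.1), so rollover ends observation at about Day 169 in both arms. That is 218 - 169 = 49 days short of Week 31, but equal between arms.

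**Observation time by arm (illustration).** Assume 24% stop on FUMADERM and 2% to 5% on risankizumab, evenly over Days 1 to 168. The mean stopping day is 84.5, so early stoppers end on average at 84.5 + 49 = 133.5 (FUMADERM) and 133.5 + 23.8 = 157.3 (risankizumab).

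- No rollover: FUMADERM 0.76 × 218 + 0.24 × 133.5 = 198 days; risankizumab 0.95 × 218 + 0.05 × 157.3 = 215, or 217 with 2% stopping. The gap is 9% to 10%.
- 90% rollover in both arms: a completer averages 0.9 × 169 + 0.1 × 218 = 173.9; the arms average 164 against 173 to 174 days, a gap of 5% to 6%.
- With FUMADERM stopping at 10% to 35%, and early, late or even stopping times, the gap runs from about 0.5% to 28%.
- Unequal rollover can move it either way. With 3% risankizumab stopping and 95% against 60% rollover, the means are 171 (risankizumab) and 175 days.

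**Patient-year denominator.** SAP 11.2.1 uses last dose - first dose + offset, with no cap. For a subject rolling over on Day 169 the sensitivity analysis credits 113 - 1 + 105 = 217 days on risankizumab and 169 - 1 + 49 = 217 on FUMADERM, against 169 - 1 = 168 to rollover: 49 days too many in each arm. In the main analysis FUMADERM is credited 169 - 1 + 7 = 175, so the excess is 49 days on risankizumab and 7 on FUMADERM.

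**The case against.** The operative rule is unambiguous: the window is defined first, and the disputed sentence only describes its result. Correcting the sentence alone changes no programmed output. Rates per 100 patient-years are already planned. Both points stand, and they keep this from being more than a moderate finding. The rates remain only a partial remedy, for the denominator reason above, and the tested proportions stay unadjusted.

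Four stronger readings are tempting and are not supported.

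- *Rollover makes follow-up unequal.* It does not by itself, since both arms end at about Week 24. Imbalance needs different rollover shares, for which the documents give no figure.
- *Risankizumab will show a spurious excess of any TEAE.* With 24% against 5% stopping evenly over Weeks 0 to 16, and one constant hazard from 73% in 48 weeks (the Phase 2 study in Protocol 3.0), a simulation gives 56.2% on risankizumab against 51.3% without rollover and 47.6% against 44.5% with full rollover. But it lets stopping be independent of adverse events, whereas the 24% is stopping because of them. Those subjects already count under any TEAE, however short their later window. Protocol 3.2 also places many gastrointestinal complaints in the initial weeks, inside either window.
- *The imbalance always runs against risankizumab.* It reverses for stops after Week 12 and before the Week 16 injection.
- *Fisher's test becomes anti-conservative.* With equal hazards, 55 per arm, 3% against 24% stopping and no rollover, expected incidences were 12.6% against 11.6%, or 58.7% against 54.5%, and the test rejected in about 3% to 4.5% of runs. The estimates shift; type I error did not exceed 5% in these cases.

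**Conclusion.** The statement of identical observation periods is wrong as written. It is exact for on-schedule completers without rollover. For early discontinuers the ends differ by -27 to +56 days, usually with longer observation on risankizumab; this is day arithmetic on the SAP's own rules. For rollover subjects only the Week 31 wording fails.

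Whether the arms end up materially unequal depends on early stopping being more frequent on FUMADERM. The cited 24% makes that plausible but does not establish it for this trial. The gap in mean observation time is illustrative and rests on assumed stopping rates, stopping times and rollover shares. The effect on any TEAE cannot be sized from the documents. It matters more for other categories, such as serious events and Areas of Safety Interest, where a subject who stopped for a different event has not already been counted.

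**What to change.** 1. In SAP 11.2.1, restrict the sentence to completers who do not roll over, and state that rollover subjects in both arms end at rollover.
2. Report adverse-event observation time by arm. Add to the sensitivity analysis a time-to-first-event comparison for any TEAE, serious events and Areas of Safety Interest, censoring each subject at the actual end of adverse-event observation. Note that censoring may be informative for individual event types, since many stops follow another adverse event.
3. Cap the patient-year denominator at rollover.
4. Reconcile Protocol Appendix C, footnote b, with Protocol 5.1, 5.4.1 and 6.1.4, so that the follow-up call time for early discontinuers is stated once for each arm. A call at 7 weeks also falls within 15 weeks, so this is a loose end in the protocol rather than evidence about the SAP analysis.

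The cost is minor wording, one change to the denominator and one extra standard table, all from dates already collected.
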